2.4. Analysis Set

All Treated analysis set includes all subjects who received at least 1 dose of study drug and will be used for safety analyses unless otherwise specified.

Eligible analysis set is a subset of the all treated analysis set that excludes ineligible subjects who did not satisfy each and every eligibility criteria for study entry. Eligible analysis set will be used for efficacy analysis unless otherwise specified.

The 11 subjects slotted to enroll in Arm C but treated per the Arm A or Arm B dose schedule will be summarized with Arm A or Arm B subjects based on actual treatment received.

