13. TREATMENT/FOLLOW-UP DECISION AT EVALUATION OF PATIENT

Patients who are CR, PR, CI, or SD will continue treatment per protocol.

Patients will be discontinued from treatment and go to event-monitoring phase per Section 4 for any of the following reasons:

- Disease progression (Except relapse that occurs during dose interruption).
- Leukemic transformation (as per WHO criteria)
- Any clinical adverse event, laboratory abnormality, intercurrent illness or other medical condition or situation which occurs such that continued participation in the study would not be in the best interest of the participant
- Hepatotoxicity criteria for treatment discontinuation (see Section [8.2.1](#))
- Pregnancy
- Diagnosis of positive status for HIV or hepatitis B or C
- Continued failure to comply with study procedures or use of the drug as specified in the study protocol such that continued participation in the study would not be in the best interest of the participant
- Withdrawal of consent
- Initiation of non-protocol therapies
- Administrative decision by investigator or sponsor

A patient is deemed *ineligible* if after registration, it is determined that at the time of registration, the patient did not satisfy each and every eligibility criteria for study entry. The patient may continue treatment off-protocol at the discretion of the physician as long as there are no safety concerns, and the patient was properly registered. The patient will go directly to the event-monitoring phase of the study.

- If the patient received treatment, all data up until the point of confirmation of ineligibility must be submitted. Event monitoring will be required per Section 4 of the protocol.
- If the patient never received treatment, on-study material and the End of Active Treatment/Cancel Notification Form must be submitted. No further data submission is necessary.

A patient is deemed a *major violation*, if protocol requirements regarding treatment in Cycle 1 of the initial therapy are severely violated that evaluability for primary end point is questionable. All data up until the point of confirmation of a major violation must be submitted. The patient will go directly to the event-monitoring phase of the study. The patient may continue treatment off-protocol at the discretion of the physician as long as there are no safety concerns, and the patient was properly registered. Event monitoring will be required per Section 4 of the protocol.

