16.3. Primary Outcome Analyses(to be evaluated in each arm independently)

Definition: The primary endpoint in each arm of this trial is the overall response rate. For Arms A, B, C, E, and F overall response is defined to be a CI, PR, or CR noted as the objective status according to the IWG-MRT consensus criteria for MF. Response in Arm G is defined as HI, PR or CR according to the IWG criteria for MDS ([Cheson et al. 2006](#)). Response in Arm D is defined by a durable (2 months or more) decrease in peripheral blood and bone marrow blast percentage to less than 5%. All patients meeting the eligibility criteria who have signed a consent form and have begun treatment will be evaluable for overall response.

Estimation: The proportion of successes will be estimated in each arm by the number of successes divided by the total number of evaluable patients. Ninety-five percent Clopper-Pearson exact binomial confidence intervals for the true success proportion will be calculated.

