4.2. Primary Efficacy Endpoint

4.2.1. Definition

The primary endpoint in each arm is the overall response rate. For Arms A, B, E, and F overall response is defined to be a CI, PR, or CR noted as the objective status according to the IWG-MRT consensus criteria for MF. Response in Arm G is defined as HI, PR or CR according to the IWG criteria for MDS (Cheson et al. 2006). Response in Arm D is defined by a durable (2 months or more) decrease in peripheral blood and bone marrow blast percentage to less than 5%. The primary outcome will be the percentage of responses observed in each arm in the eligible analysis set.

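### The primary response rate is reported only in eligible treated subjects, with no all-treated rate beside it and no stated safeguard on when eligibility is decided

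*SAP*

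**What the plan says.** SAP 2.4 defines two sets. Of the first it says: "All Treated analysis set includes all subjects who received at least 1 dose of study drug and will be used for safety analyses". The second is a subset of the first that "excludes ineligible subjects who did not satisfy each and every eligibility criteria for study entry", and its use is stated as follows: "Eligible analysis set will be used for efficacy analysis unless otherwise specified". No efficacy section specifies another set. SAP 4.2.1 is explicit for the primary endpoint: "The primary outcome will be the percentage of responses observed in each arm in the eligible analysis set". SAP 4.2.2 gives the count, percentage and exact Clopper-Pearson 95% interval by arm in that set only.

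The rule comes from the protocol. Protocol 16.3 says: "All patients meeting the eligibility criteria who have signed a consent form and have begun treatment will be evaluable for overall response".

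Protocol 13 classes a patient as ineligible when "after registration, it is determined that at the time of registration, the patient did not satisfy each and every eligibility criteria". It expects that some of these patients will already have been dosed: "If the patient received treatment, all data up until the point of confirmation of ineligibility must be submitted". They then move straight to event monitoring, and any further treatment is off-protocol. No latest date for the determination is given, and nobody is required to make it without knowledge of response.

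**The concern.** In a single-arm, open-label study the response rate is only as sound as its denominator. Here a treated patient leaves the denominator for failing any one criterion, at whatever time the failure is found, and the people who find it can know how the patient fared. If non-responders are scrutinised more closely than responders, the rate rises; the reverse lowers it.

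Most criteria are hard to reinterpret, but some rest on judgement: life expectancy and the attribution of raised transaminases to extramedullary hematopoiesis (Protocol 3.1), and uncontrolled intercurrent illness (Protocol 3.2). Protocol Table 19 also sends the initial marrow to central review together with the response biopsy for responders, and at the end of Cycle 9 or at early discontinuation for the others. That review reads blasts and ring sideroblasts, which bear on entry to Arms D, E, F and G. The documents do not say that central review alters eligibility, but such information arrives when outcome is largely known.

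Accrual closed at 80 of a maximum 148 patients, so the decision rules at 25 or 26 evaluable patients may not have been reached in Arms D to G. The reported rate and its interval then carry the result, and the plan provides only one version of it.

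**Working it through.** **1. The plan's own figures.** Protocol 16.1 states operating characteristics on evaluable patients. For the two-stage rule (at least 2 of 11, then at least 5 of 26), the probability of declaring the regimen promising is the sum over x = 2 to 11 of b(x; 11, p) × P(Y ≥ 5 − x), with Y binomial(15, p).
- Two-stage: 0.0865 at p = 0.10 (stated 0.09) and 0.8516 at p = 0.30 (stated 0.85). Early stopping at p = 0.10 is 0.6974 (stated 0.70).
- One-stage, at least 5 of 25: 0.0980 at p = 0.10 (stated 0.10) and 0.9095 at p = 0.30 (stated 0.91).

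These reproduce. The point is not an error in the design calculation.

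**2. Arm size (assumption).** Enrolled: 80 (SAP 1.3). Planned for Arms A, B and C: 34 (SAP 1.3). If exactly 34 were accrued there, Arms D to G hold 80 − 34 = 46, a mean of 46/4 = 11.5. With Arm C merged, Arms A and B average 34/2 = 17. Over the six analysis arms the mean is 80/6 = 13.3. Actual per-arm counts and numbers of ineligible subjects are not given.

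**3. Effect of one exclusion.** With x responders among n treated:
- dropping a non-responder changes the rate by x/(n − 1) − x/n = x/[n(n − 1)];
- dropping a responder changes it by (x − 1)/(n − 1) − x/n = −(n − x)/[n(n − 1)].

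The exact limits are the 2.5% quantile of Beta(x, n − x + 1) and the 97.5% quantile of Beta(x + 1, n − x).

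| Assumed arm of 12 treated | 3 responders | 4 responders |
|---|---|---|
| None excluded | 3/12 = 25.0% (5.5 to 57.2) | 4/12 = 33.3% (9.9 to 65.1) |
| One non-responder excluded | 3/11 = 27.3% (6.0 to 61.0) | 4/11 = 36.4% (10.9 to 69.2) |
| Two non-responders excluded | 3/10 = 30.0% (6.7 to 65.2) | 4/10 = 40.0% (12.2 to 73.8) |
| One responder excluded | 2/11 = 18.2% | 3/11 = 27.3% |

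The first non-responder removed adds 3/132 = 2.3 or 4/132 = 3.0 points; the second adds 3/110 = 2.7 or 4/110 = 3.6. Removing one responder instead costs 9/132 = 6.8 or 8/132 = 6.1 points.

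**4. How general this is.** With 4 of 12, one exclusion takes the lower limit from 9.9% to 10.9%, past the 10% null. That crossing is specific to this configuration: from 4/13 to 4/12 the limit goes from 9.1% to 9.9% and stays below 10%, and with 3 responders in 12 it stays below 10% throughout. In an assumed arm of 17 with 5 responders the shift is 5/(17 × 16) = 1.8 points.

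**The case against.** Much of the case on the other side stands.

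- **The SAP did not choose this set for itself.** Protocol 16.3 prespecifies the same evaluability rule, and the error rates in Protocol 16.1 are stated for evaluable patients. A reader might infer a departure from the protocol; there is none.
- **Eligibility is judged as of registration.** Many criteria are numeric laboratory limits within a 14-day window, and the registration application verifies eligibility first (Protocol 6.1). This narrows the room for discretion but does not close it, since Protocol 13 provides for later findings.
- **The set is not built to flatter.** Protocol 13 also defines major violations, whose evaluability for the primary endpoint is in doubt; SAP 2.4 does not remove them.
- **The reader is not blind to exclusions.** SAP 3.1 summarises baseline data for both sets, SAP 3.2 gives numbers treated by arm, SAP 3.4 lists major deviations and SAP 4.2.2 lists response by cycle. Eligible responders divided by all treated gives a lower bound for the all-treated rate. Missing are a tabulated rate with its interval and a dated list of eligibility decisions.

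A reader might also infer that exclusions were made with outcome known. Nothing in the documents shows this. Protocol 16.1 gives 34 to be accrued and 33 evaluable in Arms A to C, without a reason for the difference. Nor is it supported to say that two exclusions lift an arm from 25% to a threshold of 30%: the rules are 2 of 11, 5 of 26 and 5 of 25, so an observed 30% triggers nothing, and Protocol 16.1 names 20% as promising for Arm D.

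**Conclusion.** The point holds as a gap in reporting and safeguards. The sole primary analysis uses a set from which treated subjects can be removed after registration, in an open-label trial, with no deadline, no freeze before response is known and no all-treated comparison. The direction of any bias is not determined, and the documents do not show that any occurred.

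The size rests on an assumed 12 treated with 3 or 4 responders: about 2 to 4 points up per excluded non-responder, about 6 to 7 points down per excluded responder. Against exact intervals about 50 points wide these shifts are modest, and in an arm nearer 17 they are smaller. The movement of the lower limit past 10% is one illustrative case and is not a decision rule of the plan. This is a cheap improvement and does not by itself invalidate the primary analysis.

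**What to change.** In SAP 4.2.2:

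1. Report the overall response rate with exact Clopper-Pearson 95% interval by arm in the All Treated set, beside the Eligible set.
2. State how treated ineligible subjects are counted: those without a documented response are non-responders. A rule is needed because data submission may stop once ineligibility is confirmed, apart from event monitoring (Protocol 13), and SAP 4.1.2 does not impute missing values. The myelofibrosis criteria also require benefit for at least 12 weeks (Protocol Table 15), so a subject moved off early may never qualify.
3. List each exclusion from the Eligible set with the criterion failed and the date of determination.
4. Fix the Eligible set before responses are tabulated, or disclose that this was not possible. Disclosure may be the realistic option: accrual closed on 22 January 2014, 48 weeks later is December 2014 at the latest, and the SAP's amendment history shows a draft of June 30, 2017.

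The cost is one extra table and one listing. The all-treated rate may be slightly lower than the eligible rate.

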3. SUBJECT INFORMATION

3.1. Demographics and Baseline Characteristics

Demographics and disease characteristics data will be summarized for the all treated analysis set and the eligible analysis set, including sex, age (years), race, ethnicity, ECOG performance status, weight (kg), myelofibrosis subtype (primary, post ET, or post PV), DIPSS-Plus risk status, transfusion dependence, baseline laboratory values/categories, spleen and liver assessments.

The corresponding listing will also be provided.

3.2. Disposition Information

Number of subjects treated, discontinued from treatment/study, and reasons for discontinuation will be summarized by study arm for the all treated analysis set.

The corresponding listing will also be provided.

3.3. Extent of Exposure

A listing of subjects' exposure including study day, dose received, dose adjustment, corresponding reason, and other related information will be presented for all subjects in the all treated analysis set.

3.4. Protocol Deviations

A listing of subjects with major protocol deviations including cycle numbers and the type of deviation will be provided.

3.5. Prior and Concomitant Medications

Prior and concomitant medication information collected on eCRF will be listed separately for all subjects in the treated analysis set.

4. EFFICACY

4.1. Analysis Specifications

4.1.1. Level of Significance

All tests and 95% confidence intervals presented will be 2-sided.

4.1.2. Data Handling Rules

Unless specified otherwise, missing values will not be imputed.

4.2. Primary Efficacy Endpoint

4.2.1. Definition

The primary endpoint in each arm is the overall response rate. For Arms A, B, E, and F overall response is defined to be a CI, PR, or CR noted as the objective status according to the IWG-MRT consensus criteria for MF. Response in Arm G is defined as HI, PR or CR according to the IWG criteria for MDS (Cheson et al. 2006). Response in Arm D is defined by a durable (2 months or more) decrease in peripheral blood and bone marrow blast percentage to less than 5%. The primary outcome will be the percentage of responses observed in each arm in the eligible analysis set.

4.2.2. Analysis Methods

The number and percentage of responders in the eligible analysis set will be reported by each treatment arm along with 95% Clopper-Pearson exact binomial confidence intervals. Subjects' response status collected at each cycle will be listed.

4.3. Major Secondary Endpoints

4.3.1. Definition

Spleen Response

Spleen response is defined as either a minimum 50% reduction in palpable splenomegaly of a spleen that is at least 10 cm at baseline or a spleen that is palpable at less than 10 cm but more than 5 cm at baseline becomes not palpable.

Transfusion Independence

Transfusion dependency is defined by a history of at least 2 units of red blood cell transfusions in the last month or a baseline hemoglobin level of less than 85 g/L that was not associated with clinically overt bleeding. For a transfusion dependent subject, transfusion independence is defined as he/she met either of the following conditions:

- Received no more than 1 unit of red blood cell transfusions in a rolling time interval of 30 days or more.
- Had a hemoglobin level increase over baseline more than 2g/dl if his/her baseline hemoglobin level was less than 85 g/L and received no transfusion.

Time to Response (TTR)

Time to response is defined as the duration from Study Day 1 to the earliest date that a response is first documented. For non-responders, it will be censored at the date of progressive disease/relapse or the date of the last adequate assessment, whichever comes first.

Duration of Response (DoR)

Duration of response is defined for responders as the interval from date of the initial documentation of a response to the date of first documented evidence of disease progression (or relapse for subjects who experience CR). For those subjects who are still without progression/relapse, DoR will be censored at the last adequate assessment.

Overall Survival (OS)

OS is defined as the interval from Study Day 1 to the date of death from any cause. Survival time of living subjects will be censored on the last date a subject is known to be alive or lost to follow-up.

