11. TREATMENT EVALUATION

11.1. Myelofibrosis

Table 15: Revised International Working Group for Myeloproliferative Neoplasms Research and Treatment (IWG-MRT) and European LeukemiaNet (ELN) response criteria for myelofibrosis.

Response categories	Required criteria (for all response categories, benefit must last for ≥ 12 weeks in order to qualify as a response)
Complete Remission (CR)	
Bone marrow: ¹ Age-adjusted normocellularity; <5% blasts; \leqGrade 1 myelofibrosis², AND
 
Peripheral blood: Hemoglobin ≥ 100 g/L and <UNL; Neutrophil count $\geq 1 \times 10^9$/L and <UNL; Platelet count $\geq 100 \times 10^9$/L and <UNL; <2% immature myeloid cells³, AND
 
Clinical: Resolution of disease symptoms; Spleen and liver not palpable; No evidence of EMH

Partial Remission (PR)	
Peripheral blood: Hemoglobin ≥ 100 g/L and <UNL; Neutrophil count $\geq 1 \times 10^9$/L and <UNL; Platelet count $\geq 100 \times 10^9$/L and <UNL; <2% immature myeloid cells³, AND
 
Clinical: Resolution of disease symptoms; Spleen and liver not palpable; No evidence of EMH, OR
 
Bone marrow: ¹ Age-adjusted normocellularity; <5% blasts; \leqGrade 1 myelofibrosis², AND
 
Peripheral blood: Hemoglobin ≥ 85 but <100 g/L and <UNL; Neutrophil count $\geq 1 \times 10^9$/L and <UNL; Platelet count ≥ 50 but <100 $\times 10^9$/L and <UNL; <2% immature myeloid cells³, AND
 
Clinical: Resolution of disease symptoms; Spleen and liver not palpable; No evidence of EMH

Clinical Improvement (CI)	The achievement of anemia, spleen or symptoms response without progressive disease or increase in severity of anemia, thrombocytopenia or neutropenia ⁴
Anemia response	
Transfusion-independent patients: a ≥ 20 g/L increase in hemoglobin level⁵
 
Transfusion-dependent patients: becoming transfusion-independent⁶

Spleen response ⁷	
A baseline splenomegaly that is palpable at 5-10 cm, below the LCM, becomes not palpable⁸, OR
 
A baseline splenomegaly that is palpable at >10 cm, below the LCM, decreases by $\geq 50\%$⁸
 
A baseline splenomegaly that is palpable at <5 cm, below the LCM, is not eligible for spleen response
 
Confirmation by MRI or CT showing $\geq 35\%$ spleen volume reduction is recommended (but not required)

Response categories	Required criteria (for all response categories, benefit must last for ≥ 12 weeks in order to qualify as a response)

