16. STATISTICAL CONSIDERATIONS AND METHODOLOGY

Overview: This protocol will assess the efficacy of different schedules of imetelstat in six cohorts of patients with myelofibrosis (including blast-phase disease in Arm D) and one cohort of patients with MDS/MPN or MDS with spliceosome mutations or ring sideroblasts using a phase II study design in each arm independently.

Descriptive statistics will be used to summarize baseline patient characteristics, treatment administration, efficacy, and safety outcomes. Descriptive summaries of discrete data will present the number of patients and the incidence as a frequency and as a percentage. Descriptive summaries of continuous data will present the group mean, standard deviation, median, minimum, maximum, and sample size.

For regulatory reporting purposes, there are two time points for the analyses: (1) the primary analysis 48 weeks after the last patient has been enrolled, and (2) the final analysis after all patients have completed the study. A separate and detailed statistical analysis plan (SAP) developed prior to primary analysis will supersede analyses specified in the protocol. Deviations from the SAP will be noted in the final study report.

Primary Endpoint: The primary endpoint in each arm of this trial is overall response rate. Overall response will be defined as a CI, PR, or CR (for Arms A, B, C, E, and F) according to the IWG-MRT consensus criteria for MF, or as a HI, PR or CR (for Arm G) according to the IWG consensus criteria for MDS, or the achievement of <5% peripheral blood and bone marrow blast % that lasts for at least two months (for Arm D).

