16.4.2. Spleen Response

Spleen response is defined as either a minimum 50% reduction in palpable splenomegaly of a spleen that is at least 10 cm at baseline or a spleen that is palpable at less than 10 cm but more than 5 cm at baseline becomes not palpable. Spleen size will be measured by physical examination (palpable distance from the left costal margin) at baseline and as part of each response assessment. The proportion of patients achieving spleen response per the IMG-MRT criteria ([Section 11](#)) will be calculated by the number of patients who achieve spleen response divided by the total number of evaluable patients with spleen involvement at baseline (estimated to be approximately 80% of patients). Same method will be applied to splenectomized patients for assessment of hepatomegaly response. Ninety-five percent Clopper-Pearson exact binomial confidence intervals for the true proportion of patients with spleen response will be calculated.

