1.1. Trial Objectives

Primary Objective

To evaluate overall response rate in each of the six study arms (Arm A, B, D, E, F and G). The overall response rate for Arm C will be grouped with either A or B for analysis.

Response for Arms A, B, E, and F will be evaluated according to IWG-MRT criteria. For arm G, response will be according to the International Working Group response assessment as reported by Cheson et al. (2006). Response for Arm D will be defined by reduction in peripheral blood and bone marrow blast count to <5% and lasting for at least 2 months.

Secondary Objectives

- To evaluate the safety and tolerability of imetelstat in each arm (per NCI CTCAE, v4.0).
- To evaluate the efficacy of imetelstat in the reduction of spleen size, as measured by physical examination (palpable distance from the left costal margin) in each arm.
- To evaluate the efficacy of imetelstat in improving anemia or inducing red blood cell transfusion-independence in previously transfusion-dependent subjects (per IWG-MRT criteria) in each arm.
- To evaluate onset and durability of response as defined in primary and secondary endpoints in each arm.

Exploratory Objectives

[figure not shown]
- To evaluate the effect of imetelstat on bone marrow histology, karyotype, and JAK2V617F allele burden in each arm.
- To evaluate the effect of imetelstat on leukocytosis, circulating blast count (blast % x WBC), circulating immature myeloid cell count (sum of blast, promyelocyte, myelocyte, and metamyelocyte % x WBC), and thrombocytosis in each arm.

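### SAP 4.3.1 defines the secondary spleen response by size alone, without the 12-week duration in protocol Table 15 or the liver rule for splenectomized patients

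*SAP*

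**What the plan says.** SAP 4.3.1 places spleen response among the major secondary endpoints. The first limb reads "Spleen response is defined as either a minimum 50% reduction in palpable splenomegaly of a spleen that is at least 10 cm at baseline". The second is that "a spleen that is palpable at less than 10 cm but more than 5 cm at baseline becomes not palpable". Nothing is said about how long the reduction must last, about confirmation, or about IWG-MRT or Table 15.

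Protocol Section 11.1, Table 15, heads its criteria column with the rule that "for all response categories, benefit must last for ≥ 12 weeks in order to qualify as a response". Spleen response is a row of that table. Footnote 7 substitutes palpable liver in splenectomized patients.

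Protocol 16.4.2 opens with the same size wording as the SAP and also gives no duration there. It then sets the estimand as "The proportion of patients achieving spleen response per the IMG-MRT criteria", with a pointer to Section 11, and applies the same method to the liver in splenectomized patients.

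Protocol Section 16 settles which document governs the analysis: "A separate and detailed statistical analysis plan (SAP) developed prior to primary analysis will supersede analyses specified in the protocol".

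For the primary endpoint in the myelofibrosis arms, SAP 4.2.1 says "overall response is defined to be a CI, PR, or CR noted as the objective status according to the IWG-MRT consensus criteria for MF".

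**The concern.** The size sentence was carried from protocol 16.4.2 into the SAP, but the clause that tied it to Section 11 was not. The duration rule was lost with that clause. Someone programming from SAP 4.3.1 has no instruction to require anything beyond one visit. The SAP does state durations elsewhere (two months or more for Arm D response, 30 days or more for transfusion independence), so its silence on spleen can reasonably be read as any visit.

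The spleen is palpated by hand, unblinded, before each infusion in Cycles 1 to 9. That gives many chances for one low reading. Under the SAP wording a patient could be listed as a spleen responder on a single reading, while the same spleen data would not support a spleen-based clinical improvement in the primary endpoint. The SAP also keeps the objective of describing onset and durability of response for secondary endpoints, so a one-visit rule could set spleen onset dates as well.

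**Working it through.** **Comparison of the definitions**

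| Element | Table 15 | Protocol 16.4.2 | SAP 4.3.1 |
|---|---|---|---|
| Duration | At least 12 weeks | By pointer to Section 11 | None |
| Baseline exactly 10 cm | Must become impalpable | 50% reduction | 50% reduction |
| Baseline exactly 5 cm | Eligible | Not eligible | Not eligible |
| Splenectomized patients | Liver substituted | Liver substituted | Not mentioned |

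The boundary differences at 5 cm and 10 cm already exist inside the protocol, between Table 15 and 16.4.2. The SAP inherits them.

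**Illustration of size.** The plan gives no figure to reproduce, and no document gives a palpation error. The inputs are:
- Visits: nine post-baseline palpations, from before the infusions of Cycles 2 to 9 (eight) plus the end of Cycle 9 (one), with one infusion per cycle (Table 3). Arms with several infusions per cycle have more.
- True spleen size: constant at 6 to 12 cm (assumed).
- Error: normal and independent between readings, SD 1 to 3 cm (assumed). Baseline is one reading with the same error, and the patient counts if that reading exceeds 5 cm.
- Rule: SAP 4.3.1, met at any visit.

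A case that can be checked by hand has true size and baseline reading both 10 cm, so a reading of 5 cm or less qualifies. Per visit q = Φ(−5/SD), and over nine visits P = 1 − (1 − q)^9.
- SD 2 cm: q = Φ(−2.5) = 0.0062, so P = 1 − 0.9938^9 = 5.5%.
- SD 3 cm: q = Φ(−1.667) = 0.0478, so P = 1 − 0.9522^9 = 35.6%.

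Simulation lets the baseline reading vary too, which moves patients between the two limbs. The results therefore differ from the hand case:

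| Error SD | At least one qualifying reading, true size 6–12 cm |
|---|---|
| 1 cm | about 0.1% or less |
| 1.5 cm | at most 3% |
| 2 cm | 3% to 11% |
| 3 cm | 24% to 32% |

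If four consecutive readings must qualify, the rate is at most 0.3% at SD 2 cm and below 3% at SD 3 cm. Five consecutive readings give less still. With within-patient error correlation of 0.5 (assumed) and the same total SD, the single-reading rates fall to about 0.2% to 1.4% at SD 2 cm and 6% to 12% at SD 3 cm. For larger spleens they are also lower: at a true 14 cm with independent error, about 0.8% at SD 2 cm and 14% at SD 3 cm.

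**What 12 weeks means in visits.** Twelve weeks is 84 days. On 21-day cycles, 84/21 = 4 intervals, so five consecutive visits. On 28-day cycles, 84/28 = 3 intervals, so four visits.

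**Late responses.** Table 3 requires no spleen examination in the Extension Phase. Nine 21-day cycles end 189 days after the first dose, so a reduction must be seen by day 189 − 84 = 105 to have 12 weeks of scheduled core-phase readings. On 28-day cycles the figures are 252 − 84 = 168 days.

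**The case against.** The strongest reply is that little rests on this definition. SAP 4.3.2 only lists spleen status; the SAP plans no spleen response rate, interval or test. Spleen assessments are listed separately (SAP 4.3.3), so a reader could judge durability. The size sentence comes from protocol 16.4.2, and the clause on precedence speaks of analyses, not of the Section 11 criteria. All of this stands, and it limits the consequence. It does not supply the missing rule: listed status must still be derived from SAP 4.3.1, and a rate of the kind protocol 16.4.2 plans would inherit the wording.

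A reader might also infer more than the documents support:
- **That the primary response rate is inflated.** It is not. SAP 4.2.1 cites IWG-MRT, which carries the 12 weeks.
- **That the SAP prescribes the best single reading.** It is silent. The wording permits a one-visit response but does not instruct it.
- **That every disagreement between spleen status and clinical improvement comes from this gap.** Table 15 and footnote 4 also require no progression, no worsening of anemia, thrombocytopenia or neutropenia, and minimum counts. The two can differ even under a 12-week rule.
- **That a quarter or more of unchanged spleens would be counted as responses.** That needs an error SD of 3 cm with independent readings. Neither comes from the documents.

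**Conclusion.** The inconsistency is real and rests on the text alone: SAP 4.3.1 keeps the size thresholds, drops the link to Section 11 and with it the 12 weeks, and omits the liver substitution. As written, one qualifying palpation meets the definition.

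The reach is limited to the secondary spleen endpoint, meaning its listed status and any rate, onset or duration taken from it. The numerical effect is unknown. Under the assumed error model it runs from negligible at SD 1 cm to 24% to 32% at SD 3 cm for unchanged spleens of 6 to 12 cm, and correlation between readings reduces it. The direction is not in doubt, because a one-visit rule can only count as many patients as a sustained rule on the same thresholds, or more. This is worth correcting because the change is simple, not because a main conclusion depends on it.

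**What to change.** In SAP 4.3.1, define spleen response by reference to protocol Table 15, stating:
1. The reduction must last at least 12 weeks.
2. The size boundaries are those of Table 15, so that baselines of exactly 5 cm and exactly 10 cm are classified the same way everywhere.
3. In splenectomized patients, palpable liver is substituted with the same measurement strategy.
4. The 12 weeks are derived from assessment dates, with every reading in the period qualifying (five consecutive visits on 21-day cycles, four on 28-day cycles), and with a stated treatment of the ±3-day visit window.
5. Reductions first seen too late for 12 weeks of scheduled readings are listed as unconfirmed, not as responses.

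If a one-visit definition is intended, say so, justify it, and label the listing so that it is not read as IWG-MRT spleen response.

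The cost is SAP wording and slightly more derivation work. No new assessments are needed, given the rule for late reductions. Fewer patients may be listed as spleen responders.
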